1.4 Objective

To evaluate the efficacy of Baan HUG-M in decreasing sexual risk behavior; increasing HIV testing to at least biannually; and increasing prompt, sustained engagement in care among YMSM living with HIV by using a longitudinal cohort of YMSM in Ubon Ratchathani and Mahasarakham

2. Study design and methods of data collection

This study aims to evaluate the effectiveness of the Baan HUG-M intervention, a community-based strategy designed to promote HIV prevention and facilitate access to care among young men who have sex with men (YMSM) aged 15 to 29 years. A longitudinal cohort design is employed across two geographic locations: Ubon Ratchathani (intervention site) and Mahasarakham (control site), with a total sample size of 600 participants (300 per site). The follow-up period spans 24 months, with data collection occurring at five time points: baseline and months 6, 12, 18, and 24.

Data collection comprises self-administered surveys completed via the Qualtrics platform⁷ and self-collected biological specimens, including urine samples and rectal swabs, for chlamydia and gonorrhea testing. All specimens will be transported to and analyzed at the Office of Disease Prevention and Control 10 (ODPC 10), located in Ubon Ratchathani Province. Additionally, study data will be linked to the national HIV database maintained by the Ministry of Public Health. To protect participant confidentiality, no personally identifiable information is collected within the survey. Instead, a Unique Identification Code (UIC) is assigned to each participant to enable secure and systematic linkage of data across multiple sources.

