2.2 Eligibility criteria

Inclusion Criteria:

- Aged between 15 and 29 years
- Currently residing, studying, or working in either Warin Chamrap District or Mueang District of Ubon Ratchathani Province (intervention site), or in Kantharawichai District or Mueang District of Mahasarakham Province (control site)
- Intend to remain in the study area for at least the next three years
- Assigned male at birth
- Self-identify as gay, men who have sex with men (MSM), bisexual, or *toot* (a locally understood term)
- Have engaged in anal sex (insertive or receptive) with a male partner within the past 12 months
- Willing and able to provide informed consent to participate in the study

Exclusion Criteria:

- Aged ≤ 14 years or ≥ 30 years
- Not currently residing, studying, or working in one of the designated study areas
- Planning to move out of the study area within the next three years
- Assigned female at birth
- Self-identify as a woman, transgender woman, or transfeminine individual
- Unwilling to participate in follow-up activities associated with the study

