2.4.1 Descriptive Analyses

Baseline demographic, behavioral, and health characteristics of participants will be summarized using descriptive statistics, stratified by study arm (intervention vs. control). Comparisons will be made between the two study sites (Ubon Ratchathani as the intervention site, and Mahasarakham as the control site) to assess initial differences and changes over time. Categorical variables will be presented as frequencies and percentages. Continuous variables will be summarized using means and standard deviations, or medians with interquartile ranges (25th to 75th percentile), depending on data distribution.

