2.4.2 Primary and Secondary Outcome Analyses

To evaluate the effects of the intervention over time, Generalized Estimating Equations (GEE) with appropriate link functions will be applied (e.g., logit for binary outcomes and identity for continuous outcomes). The models will include study arm, time (follow-up round), and their interaction to estimate the effect of the intervention across time points. Robust standard errors will be used to account for within-subject correlation due to repeated measurements. For incidence outcomes (e.g., HIV, chlamydia, and gonorrhea infections), person-time will be calculated, and incidence rate ratios (IRRs) with 95% confidence intervals will be reported.

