1.2 Background and Significance of the Study

This study aims to evaluate the efficacy of the BAAN HUG-M intervention in:

- Reducing sexual risk behaviors
- Increasing the frequency of HIV testing (at least biannually)
- Promoting prompt and sustained engagement in HIV care

The study is conducted through a longitudinal cohort of young men who have sex with men (YMSM) (“YMSM Cohort”, $N = 600$) residing in Ubon Ratchathani (intervention site) and Mahasarakham (control site). Given the disproportionate burden of HIV among YMSM in Thailand, and the structural and behavioral barriers to care, this study addresses a critical public health challenge with implications for national HIV policy and intervention programming.¹⁻³

2. Study Design Overview

This will be a prospective, longitudinal cohort study involving 600 young men who have sex with men (YMSM) aged 15–29 years, with equal allocation to two study sites:

- Intervention city: Ubon Ratchathani ($n = 300$)
- Control city: Mahasarakham ($n = 300$)

Participants will be followed for 24 months, with data collection scheduled at five time points: baseline, 6 months, 12 months, 18 months, and 24 months.

Data Collection and Sources

Data will be collected through online self-administered questionnaires hosted on the Qualtrics platform and completed using tablets or smartphones. To ensure anonymity while enabling longitudinal data linkage, no personal identifiers will be recorded. Instead, participants will enter a Unique Identification Code (UIC) at each round of data collection.

Retention and Follow-up

To promote high retention throughout the study period, the research team will implement continuous engagement strategies via digital platforms and peer-led community outreach. These efforts are expected to result in follow-up retention rates of greater than 60% at each follow-up time point.

3. Study Objectives and Endpoints

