3.3 Primary Outcome

- **HIV testing uptake:**

Proportion of participants who report having ever tested for HIV during the 24-month follow-up period. Data will be collected from HIV testing records provided by the Ministry of Public Health national database.

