6.2 Primary and Secondary Outcome Analyses

To evaluate the effects of the intervention over time, Generalized Estimating Equations (GEE) with appropriate link functions (e.g., logit for binary outcomes, identity for continuous outcomes) will be used.⁸ The models will include study arm (intervention vs. control), time (follow-up visits), and their interaction term to estimate intervention effects over time. Robust standard errors will be used to account for within-subject correlation. Person-time will be calculated and compared using rate ratios and 95% confidence intervals.

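### Arm is the same as city and no randomisation is described, yet no baseline adjustment is prespecified for the primary testing outcome or the incidence rate ratios

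*Combined protocol and SAP*

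**What the plan says.** **Design.** Protocol section 2 describes a longitudinal cohort "across two geographic locations: Ubon Ratchathani (intervention site) and Mahasarakham (control site"). Membership is an eligibility matter: protocol 2.2 requires a man to be "Currently residing, studying, or working in either Warin Chamrap District or Mueang District of Ubon Ratchathani Province (intervention site"), or the equivalent for the two control districts. SAP section 2 speaks of 600 men "with equal allocation to two study sites", 300 in each. Protocol 2.5 calls the study observational. No section describes random allocation of men or of cities.

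**Models.** Protocol 2.4.2 states: "The models will include study arm, time (follow-up round), and their interaction". SAP 6.2 repeats this: "The models will include study arm (intervention vs. control), time (follow-up visits), and their interaction term to estimate intervention effects over time". On variance it adds: "Robust standard errors will be used to account for within-subject correlation". For HIV, chlamydia and gonorrhea incidence, protocol 2.4.2 plans rate ratios from person-time. SAP 6.2 does the same without naming the outcomes. Neither names a covariate.

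**Primary outcome.** SAP 3.3 defines it as "Proportion of participants who report having ever tested for HIV during the 24-month follow-up period". The primary objective (SAP 3.1) concerns men never tested before, whereas the primary analysis population (SAP 4.1) is everyone who completed baseline.

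**Use of baseline data.** Protocol 2.4.1 compares the sites "to assess initial differences and changes over time", as description. SAP 7.1 lists age group, exposure level and Province as subgroups to be tested by interaction. The only sensitivity analysis in SAP 7.2 changes the link function or the model type.

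**The concern.** When arm is fixed by location, the two groups can differ at entry in ways that bear on the outcome. The plan looks at such differences at baseline but never carries them into a main model: it has no covariate list, weighting, matching or standardisation. The age-group interactions would give age-specific effects, not an age-adjusted main estimate. Multiple imputation and pattern-mixture models (SAP 5.1) deal with missing data, not with confounding.

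If the plan is followed as written, the headline result on testing and the incidence rate ratios are unadjusted contrasts of two cities. A difference in age mix, or in testing history if all baseline completers are analysed, would pass as an effect of BAAN HUG-M. If covariates are added later without being named in advance, their choice could follow the results.

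**Working it through.** The documents give no effect size, control rate, power or sample-size derivation, so there is no planned figure to reproduce beyond 300 + 300 = 600. The check is mainly structural, followed by an illustration on assumed values.

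**1. Where arm × time removes a city difference.**

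| Outcome | Value at baseline? | Can arm × time remove a stable city difference? |
|---|---|---|
| Condomless anal intercourse, PrEP use | Yes, if asked in the baseline questionnaire | Yes, on the model scale, if baseline is a modelled visit |
| Testing during 24 months (SAP 3.3), read as cumulative | No, it starts at enrolment | No |
| HIV, chlamydia and gonorrhea rate ratios | No pre-enrolment person-time | No |

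If the primary analysis is limited to never-tested men, ever-tested status at baseline is zero in both cities. There is then no baseline difference to subtract, even in a by-visit model. The restriction controls testing history but not age or other characteristics.

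**2. Illustration of the consequence, with no intervention effect.** From the documents: 300 men per city. Assumed: mean uptake 50%; two age strata; shares of older men in the two cities 20 points apart (60% and 40%); a gap in follow-up uptake between strata of 10, 20 or 28.3 points. The last value is borrowed from protocol 1.2 (73.3% never tested at ages 15–19, 45% at 20–24; 73.3 − 45 = 28.3). That gap concerns past testing and does not measure a gap in uptake during this study.

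- Bias = gap × mix difference: 0.10 × 0.20 = 2.0 points; 0.20 × 0.20 = 4.0 points; 0.283 × 0.20 = 5.66, about 5.7 points.
- Pooled standard error = √(2 × 0.5 × 0.5 / 300) = 0.0408.
- Bias / SE = 0.49; 0.98; 1.39.
- Two-sided rejection = Φ(bias/SE − 1.96) + Φ(−bias/SE − 1.96) = 7.8%; 16.5%; 28.3%.
- Simulation of the same settings (400,000 runs per cell) gives 7.9%, 16.6% and 28.6% unadjusted. The Mantel-Haenszel age-stratified test gives 5.0% to 5.1%, with mean bias about 0.
- Halving the mix difference to 10 points halves the bias to 1.0 / 2.0 / 2.8 points, and rejection falls to 5.7% / 7.8% / 10.7%.

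**3. Province interaction.** With five time points, the main model has 1 intercept + 1 arm + 4 time + 4 arm × time = 10 columns, rank 10. Adding Province (1), arm × Province (1), Province × time (4) and arm × Province × time (4) gives 20 columns. The rank stays 10, so no Province term can be estimated. The age-group terms are estimable (30 columns, rank 30).

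**4. One city per arm.** Between-city variance needs at least two cities in some arm; here it has 0 degrees of freedom. The robust standard errors cover repeated measures within a man and nothing between cities.

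**The case against.** Four points on the other side deserve weight.

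- *The GEE already handles baseline differences.* SAP 6.2 applies a by-visit model to primary as well as secondary outcomes. If ever-tested status were modelled at each round including baseline, in all participants, stable city differences would drop out on the logit scale. This stands as a possible reading. But SAP 3.3 counts testing during follow-up, neither document says that baseline is a modelled visit for this outcome, and the route closes if the analysis is limited to never-tested men. It does nothing for the rate ratios.
- *The plan is open about its design.* It calls itself an observational cohort and names one city per arm. That is fair: the wording about allocation and assignment describes site membership and should not be read as a claim of randomisation. What is missing is a statement that inference is conditional on the two cities.
- *The size is assumed.* This also stands. Both cities share the same age limits and recruitment plan, and no section gives an age mix for either. A reader might take the 28.3-point gap as evidence of large bias. It is a gap in past testing, for which older men have had more years, and it says nothing about later uptake among men who have never tested.
- *The Province item is harmless.* Largely so. A reader might infer that it damages the main results, but redundant terms would simply be dropped and no main estimate is biased.

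**Conclusion.** The omission is certain from the text: neither document prespecifies any baseline adjustment for a comparison in which arm is city. It matters for the primary testing outcome, on the cumulative reading of SAP 3.3, and for the incidence rate ratios. It should be settled before outcome data are analysed.

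The size of the bias is unknown. The 2.0 to 5.7 points, and rejection of about 8% to 28% at a nominal 5%, rest on the assumed uptake, age gaps and 20-point mix difference. They show that a moderate imbalance could matter, not that one exists.

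Two stronger readings are not supported. The documents do not show that every outcome is confounded, because arm × time can deal with stable city differences where a baseline value is modelled. Nor would adjustment make this a clean estimate of effect: it handles measured individual differences only, and differences between the cities themselves cannot be separated from the intervention by any analysis of two cities. The Province interaction cannot be estimated, which is a minor correction.

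**What to change.** 1. In SAP 6.2 and protocol 2.4.2, make the main analysis of the primary outcome and of the rate ratios adjusted for a short, named list of baseline variables:
   - age group;
   - HIV testing history before enrolment, taken from the national database as of the enrolment date (not needed if the analysis is limited to never-tested men);
   - condomless anal intercourse at baseline, if the baseline questionnaire asks it;
   - for the chlamydia and gonorrhea rate ratios, the baseline result for those infections.

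   Use Poisson models with a person-time offset for the rate ratios. Report the unadjusted estimates as secondary. State that baseline is a time point in the models for repeated outcomes.
2. Delete Province from the interaction subgroups in SAP 7.1 (minor).
3. State that confidence intervals and p-values are conditional on these two cities, and word the conclusion as a non-randomised comparison of two cities.

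The cost is a wording change in both documents, one database extraction as of enrolment, a few more model runs and a more cautious conclusion.

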6.3 Multiple Comparisons and p-value Adjustment

If multiple statistical comparisons are conducted for secondary outcomes or subgroup analyses, adjustments for multiple testing will be considered using methods such as Bonferroni or false discovery rate (FDR) correction to control for type I error.

6.4 Statistical Software

All analyses will be conducted using STATA (version 18.0), which is the primary software tool used by the research team for data management, descriptive statistics, regression modeling, and longitudinal analyses.

7. Subgroup and Sensitivity Analyses

7.1 Subgroup Analysis

Subgroup analysis will be conducted to explore whether the effects of the intervention vary across specific participant characteristics. Pre-specified subgroups will include:

- Age groups (15–19, 20–24, 25–29 years)
- Level of exposure to the BAAN HUG-M intervention (high vs. low/moderate — intervention site only)
- Province (Ubon Ratchathani vs. Mahasarakham)

Interaction terms will be incorporated into the GEE models to evaluate whether intervention effects differ significantly across these subgroups.

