2.4 Data analysis

Both descriptive and inferential statistical methods will be employed to evaluate the effectiveness of the Baan HUG-M intervention over the study period. Analyses will compare the intervention group (Ubon Ratchathani) and the control group (Mahasarakham) across demographic variables, behavioral measures, and health-related outcomes associated with HIV and sexually transmitted infections (STIs).

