4.1 Intention-to-Treat (ITT) Population

The ITT population will include all participants who completed the baseline assessment and were assigned to either the intervention or control site, regardless of their level of

participation in the intervention activities thereafter. This population will serve as the primary analytic population for evaluating the effectiveness of the intervention, reflecting real-world implementation outcomes.

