4.2 High Exposure Subgroup

This subgroup will include participants from the intervention site who reported a high level of engagement with the BAAN HUG-M intervention activities at each follow-up round. This subgroup will be analyzed separately to evaluate the impact of sustained and intensive participation on health behaviors and outcomes.

5. Data Management and Quality Assurance

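### SAP 7.1 lists a province interaction that cannot be estimated, because province is the study arm, and treats a self-selected exposure contrast within one city as a difference in intervention effects

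*Combined protocol and SAP*

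**What the plan says.** SAP 7.1 names three subgroups: age group, exposure and province. Province is entered as "Province (Ubon Ratchathani vs. Mahasarakham". Exposure is entered as "Level of exposure to the BAAN HUG-M intervention (high vs. low/moderate — intervention site only". One sentence then covers all three: "Interaction terms will be incorporated into the GEE models to evaluate whether intervention effects differ significantly across these subgroups". No separate model is given for any of them.

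SAP 4.2 defines the high-exposure group as "participants from the intervention site who reported a high level of engagement with the BAAN HUG-M intervention activities at each follow-up round", and says that this group "will be analyzed separately to evaluate the impact of sustained and intensive participation on health behaviors and outcomes".

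The arms are defined by city throughout (protocol 2 and 2.4; SAP 2 and 6.1). Protocol 2.4 puts it this way: "Analyses will compare the intervention group (Ubon Ratchathani) and the control group (Mahasarakham". The outcome model in SAP 6.2 contains arm, time and their interaction, and no covariates. Of the ITT population, SAP 4.1 says: "This population will serve as the primary analytic population for evaluating the effectiveness of the intervention".

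**The concern.** An interaction test of effect modification needs both arms represented at each level of the subgroup variable. Of the three listed variables, only age group meets that condition.

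For province, the planned test does not exist. The most that software could return is the arm effect under another name. On its own this is a clean-up.

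Exposure carries the interpretive risk. Men place themselves in the high or low/moderate group by what they report doing after baseline. Those who engage more may already be more inclined to test, or may be at higher risk and have more infections. A contrast between such groups, unadjusted, would be reported under 7.1 as a difference in intervention effect and under 4.2 as the impact of participation. Neither description fits what is being compared.

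**Working it through.** The documents give no figure for the subgroup analyses, so there is none to reproduce. The check has three parts.

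**1. What can be estimated.** Inputs: two arms, each one city (SAP 2); five time points (SAP 2); arm, time and arm × time in the model (SAP 6.2). A model saturated in group and visit can have no more independent parameters than there are distinct group-by-visit cells. Columns and rank were computed with visit as a categorical factor. The second figure in each pair applies if only the four follow-up visits are modelled.

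| Model | Distinct cells | Columns | Rank |
|---|---|---|---|
| arm × time | 2 × 5 = 10 (2 × 4 = 8) | 10 / 8 | 10 / 8 |
| plus province and all its interactions | still 10 (8) | 20 / 16 | 10 / 8 |
| plus exposure and all its interactions, exposure = 0 in controls | 3 × 5 = 15 (3 × 4 = 12) | 20 / 16 | 15 / 12 |
| exposure × time, Ubon Ratchathani only | 2 × 5 = 10 (2 × 4 = 8) | 10 / 8 | 10 / 8 |
| arm × age group × time | 2 × 3 × 5 = 30 (2 × 3 × 4 = 24) | 30 / 24 | 30 / 24 |

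Province adds columns and no information. Exposure adds five independent parameters (15 − 10), which is a three-group comparison over time of control, low/moderate and high. The within-city exposure model also has full rank. Neither exposure model contains an arm-by-exposure term. The age interaction is fully estimable.

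**2. What self-selection alone could produce.** All inputs here are assumptions; the documents give none. Suppose that exposure has no effect on testing, that a share *s* of men is more inclined to test, that 24-month testing is *a* in them and *b* in the rest, and that inclined men are more often in the high group. Then

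apparent difference = (a − b) × [P(inclined | high) − P(inclined | low/moderate)].

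The grid was *s* = 0.3, 0.5, 0.7; *a* = 0.6, 0.7, 0.8; *b* = 0.4; probability of high exposure in inclined / other men = 0.40/0.30, 0.50/0.25, 0.60/0.20.

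- Middle (*s* = 0.5, *a* = 0.7, 0.50/0.25): P(inclined | high) = 0.25/0.375 = 0.667; P(inclined | low/moderate) = 0.25/0.625 = 0.400; 0.3 × 0.267 = 8.0 points.
- Smallest (*s* = 0.7, *a* = 0.6, 0.40/0.30): 0.28/0.37 = 0.757; 0.42/0.63 = 0.667; 0.2 × 0.090 = 1.8 points.
- Largest (*s* = 0.5, *a* = 0.8, 0.60/0.20): 0.30/0.40 = 0.750; 0.20/0.60 = 0.333; 0.4 × 0.417 = 16.7 points.

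Every scenario in the grid has test-inclined men engaging more. If they engaged less, the sign would reverse. Swapping the middle case to 0.25/0.50 gives 0.125/0.375 = 0.333 and 0.375/0.625 = 0.600, so 0.3 × (−0.267) = −8.0 points.

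**3. Attendance.** The definition in 4.2 can mean high at every round, or high as judged round by round. Under the first reading, a man who misses a round has no report for it, and the high group may be selected on attendance as well as engagement. SAP 2 says of retention: "These efforts are expected to result in follow-up retention rates of greater than 60% at each follow-up time point". If exactly 60% held within Ubon Ratchathani at a given round, at most 0.60 × 300 = 180 men could have reported at every round. That is conditional: the expectation is for more than 60% and is not given by city. If it is study-wide, 0.60 × 600 = 360, which could include all 300 men in Ubon Ratchathani.

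**The case against.** The best defence is that most of this is already contained. SAP 7.1 describes the purpose as exploratory, 4.2 analyses high exposure separately, 4.1 makes ITT primary, and 6.3 allows for multiplicity adjustment. That stands as a limit on severity. It does not remove the fault: 7.1 still pre-specifies a province test that cannot be run and speaks of effects differing significantly, and 4.2 still speaks of impact. Multiplicity adjustment cures neither aliasing nor self-selection.

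Some stronger readings are tempting and should not be drawn.

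- *That the exposure analysis cannot be estimated.* The restriction to the intervention site means that no arm-by-exposure term is called for. The within-city contrast is a fair reading of 7.1 and has full rank, as does the three-group contrast. The fault for exposure is one of interpretation.
- *That a man who misses a round is certainly excluded from the high group.* SAP 5.1 plans multiple imputation or maximum likelihood, with pattern-mixture sensitivity analyses, and does not say whether these cover exposure classification. The point is unresolved, and it depends on the every-round reading.
- *That the plan's own retention figure caps the high group at 180.* It does so only with the added assumption of exactly 60% within Ubon Ratchathani.
- *That the age interaction is faulty too.* Having one city per arm means that city differences in trend could affect any arm comparison, including the main one. That is a general feature of the design and not a defect of 7.1.

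**Conclusion.** The point holds for both variables, for different reasons. For province, no interaction is estimable (rank 10 with or without it); this follows from the design and needs no assumption. For exposure, the contrast can be computed but is an unadjusted comparison of groups self-selected after baseline, and the documents' wording claims more than it can show. The size of any bias is unknown. The range of about 2 to 17 points rests wholly on assumed inputs and on one direction of selection, so it shows only that the mechanism can produce a noticeable difference where exposure does nothing. A further selection on attendance is possible but not established.

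A reader might infer that the main result is compromised. It is not: the arm-by-time model in SAP 6.2 and the ITT population in 4.1 do not depend on these subgroups. The change should be made, but it concerns secondary, exploratory analyses.

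**What to change.** - Delete province from the list in SAP 7.1.
- Take exposure out of the interaction-term sentence. In 7.1 and 4.2, describe it as an exploratory, non-causal association within Ubon Ratchathani, adjusted for baseline covariates already collected, and replace *impact* with *association*.
- In the same edit, fix the exposure classification before analysis: the cut-off for high (the supplied text gives none), whether it must be met at every round or is judged round by round, how men who miss a round are classed, and whether the methods in SAP 5.1 apply to that classification.
- Keep age group as the arm-by-subgroup interaction.

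The cost is SAP wording and one small adjusted within-city analysis, with no new data. The downside is that a causal claim about exposure is given up. Baseline adjustment removes only measured differences, so the result stays exploratory.
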